- m. Clinical chemistry panel including CK (fasted at least 8 hours), coagulation parameters, CBC, and UA will be performed at Screening, Check-in (Day -1), Days 4 and 7, and Days 11, 16, and 20 (before rifampin dosing), and at EOT (Day 24) or ET.
- n. Hemoglobin A1c test performed at Screening only.
- o. Alcohol breath test and drugs of abuse urine test, including cotinine. Results from the alcohol and drug tests will be used to determine subject eligibility per the inclusion/exclusion criteria.
- p. Prior and concomitant medication administration will be recorded beginning at informed consent. In addition, all Investigator-approved medications taken by a subject within 30 days prior to study drug administration for prescription medications, and 14 days prior to study drug administration for non-prescription medications, will be recorded on the subject's electronic Case Report Form.
- q. Female subjects only.
- r. Post-menopausal female subjects only.
- s. EOT is defined as when the subject is released from the CRU following completion of all assessments through Day 24. ET is defined as when the subject is released from the CRU if the subject terminates the study early. Vital signs, ECG, and safety laboratory results for clinical chemistry, hematology, coagulation, and UA are to be available for review by the Investigator or designee prior to subject release from the CRU at the EOT or ET visit.
- t. To be performed 7 days (± 2 days) following EOT or ET. EOS is defined as when the CRU contacts the subject by a follow-up phone call 7 days (± 2 days) after the EOT visit or ET visit to determine if any SAE or study drug-related AE has occurred since the EOT or ET visit. All subjects who received LOXO-305 (including subjects who are terminated early) will be contacted.

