- e. 12-lead ECGs will be collected after the subject has rested in the supine position for at least 10 minutes, and will be obtained prior to and as close as possible to the scheduled blood draws at Screening and Day -1, Day 1 (predose and 2 hours after LOXO-305 dosing), Day 4 (ie, 72 hours after LOXO-305 dosing on Day 1), Day 8 (ie, 168 hours after LOXO-305 dosing on Day 1), Day 12 (before LOXO-305 and itraconazole dosing), Day 15 (ie, 72 hours after LOXO-305 and itraconazole dosing on Day 12), and at EOT/Day 19 (168 hours after LOXO-305 and itraconazole dosing on Day 12).
- f. Vital signs measurements (oral temperature, respiratory rate, and supine BP and pulse rate) will be obtained at Screening and Day -1, Day 1 (predose and 2 hours after LOXO-305 dosing), Day 4 (ie, 72 hours after LOXO-305 dosing on Day 1), Day 8 (ie, 168 hours after LOXO-305 dosing on Day 1), Day 12 (before LOXO-305 and itraconazole dosing), Day 15 (ie, 72 hours after LOXO-305 and itraconazole dosing on Day 12), and at EOT/Day 19 (168 hours after LOXO-305 and itraconazole dosing on Day 12). Vital signs measurements should be carried out prior to and as close as possible to having blood drawn. Blood pressure and pulse rate will be measured using the same arm for each reading after the subject has been supine for at least 5 minutes.
- g. An HDYF? inquiry will be performed at Screening (after the ICF is signed), at Check-in (Day -1), at each postdose vital signs assessment, and at an appropriate time for all other days.

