 Image: Abbreviations: AE = adverse event; BMI = body mass index; BP = blood pressure; CK = creatine kinase; CRU = Clinical Research Unit; ECG = electrocardiogram; EOS = End of Study; EOT = End of Treatment; ET = Early Termination; FSH = follicle-stimulating hormone; HbA1c = hemoglobin A1c; HDYF? = How Do You Feel?; HIV = human immunodeficiency virus;

ICF = Informed Consent Form; PK = pharmacokinetic; QD = once daily; SAE = serious adverse event; TSH = thyroid-stimulating hormone; UA = urinalysis.

a. For details on study procedures, see Section 7.

b. Interim medical history only.

c. Weight and BMI (based on Screening height) only.

d. A complete physical examination will be performed at Screening. An abbreviated physical examination will be performed at Check-in (Day -1) and at EOT (Day 24).

e. 12-lead ECGs will be collected after the subject has rested in the supine position for at least 10 minutes, and will be obtained prior to and as close as possible to the scheduled blood draws at Screening and Day -1, Day 1 (predose and 2 hours postdose after LOXO-305 dosing), Day 4 (72 hours after LOXO-305 dosing), Day 8 (168 hours after LOXO-305 dosing and predose of

Protocol	CONFIDENTIAL
Covance Study: 8419666	Protocol Reference: LOXO-BTK-20006

LOXO-305 and rifampin dosing), Day 11 (72 hours after LOXO-305 and rifampin dosing). Day 17 (predose of LOXO-305 and rifampin dosing), Day 20 (72 hours after LOXO-305 and rifampin dosing), and at EOT (168 hours postdose [ie, Day 24] of LOXO-305 and rifampin dosing).

- f. Vital signs measurements (oral temperature, respiratory rate, and supine BP and pulse rate) will be obtained at Screening and Day -1, Day 1 (predose and 2 hours after LOXO-305 dosing), Day 4 (72 hours after LOXO-305 dosing), Day 8 (168 hours postdose (LOXO-305 dosing and predose of LOXO-305 and rifampin dosing), Day 11 (72 hours after LOXO-305 and rifampin dosing). Day 17 (predose of LOXO-305 and rifampin dosing), Day 20 (72 hours after LOXO-305 and rifampin dosing), and at EOT (168 hours postdose [ie, Day 24] of LOXO-305 and rifampin dosing). Vital signs measurements should be carried out prior to and as close as possible to having blood drawn. Blood pressure and pulse rate will be measured using the same arm for each reading after the subject has been supine for at least 5 minutes.

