7.3. Pharmacokinetic Population

The PK population will include all subjects who received at least 1 dose of LOXO-305, have at least 1 quantifiable PK concentration, and for whom at least 1 PK parameter can be computed. A subject may be excluded from the PK summary statistics and statistical analysis if the subject has an AE of vomiting that occurs at or before 2 times the median t_{max} .

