8.6. Safety and Tolerability Assessments

8.6.1. Adverse Events

All AEs will be coded using the Medical Dictionary for Regulatory Activities (MedDRA) Version 22.1. All AEs will be assigned severity grade using National Cancer Institute Common Terminology Criteria for Adverse Events (CTCAE) Version 5.0.

A treatment-emergent adverse event (TEAE) will be defined as an AE that starts during or after the first dose, or starts prior to the first dose and increases in severity after the first dose.

A treatment-related TEAE will be defined as a TEAE with a relationship of related to the study treatment (LOXO-305 or itraconazole or rifampin), as determined by the investigator.

For Part 1 of this study, the assignment of TEAEs to the associated treatments will be as follows:

- A TEAE occurring during or after Day 1 dosing and prior to Day 8 dosing will be assigned to 200 mg LOXO-305
- A TEAE occurring during or after Day 8 dosing and prior to Day 12 dosing will be assigned to 200 mg itraconazole
- A TEAE occurring during or after Day 12 dosing will be assigned to 200 mg LOXO-305 and/or 200 mg itraconazole

For Part 2 of this study, the assignment of TEAEs to the associated treatments will be as follows:

- A TEAE occurring during or after Day 1 dosing and prior to Day 8 dosing will be assigned to 200 mg LOXO-305
- A TEAE occurring during or after Day 8 dosing will be assigned to 200 mg LOXO-305 and/or 600 mg rifampin

All AEs will be listed. In addition to the data recorded in the database, the listings will include derived onset time and duration. Onset time will be calculated from the time of the last dose for TEAEs only.

The frequency of subjects with TEAEs and the number of TEAEs will be summarized for the following categories:

- TEAEs (overall, serious, and leading to discontinuation) by treatment
- TEAEs by severity and treatment

- Treatment-related TEAEs (overall, serious, and leading to discontinuation) by treatment
- Treatment-related TEAEs by severity and treatment

The frequency of subjects will be summarized separately for TEAEs and treatment-related TEAEs by the following:

- System organ class, preferred term, and treatment
- Preferred term and treatment
- System organ class, preferred term, day of onset, and treatment

For the AE data the following rules will apply:

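### Only LOXO-305 given alone has a required adverse event inquiry on the dosing day after the dose (at 2 hours); none of the three co-administered doses has one until the next calendar day

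*Protocol*

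**What the plan says.** Footnote g in both parts of Appendix 4, repeated in Protocol Section 7.2.1, sets the HDYF? inquiry at Screening after consent, at Check-in, and then "at each postdose vital signs assessment, and at an appropriate time for all other days". The HDYF? row is marked on every study day in both parts.

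Footnote f sets the vital signs to which the inquiry is tied:

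- Part 1, LOXO-305 alone: "Day 1 (predose and 2 hours after LOXO-305 dosing), Day 4 (ie, 72 hours after LOXO-305 dosing on Day 1".
- Part 1, with itraconazole: "Day 12 (before LOXO-305 and itraconazole dosing), Day 15 (ie, 72 hours after LOXO-305 and itraconazole dosing on Day 12".
- Part 2, LOXO-305 alone: "Day 1 (predose and 2 hours after LOXO-305 dosing), Day 4 (72 hours after LOXO-305 dosing".
- Part 2, first rifampin dose: one set, "Day 8 (168 hours postdose (LOXO-305 dosing and predose of LOXO-305 and rifampin dosing"; the next is on Day 11, at 72 hours.
- Part 2, repeated rifampin: predose on Day 17, then Day 20, at 72 hours.

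Section 7.2.1 also says that the question covers the time since the subject was last asked and that subjects are encouraged to report events at any other time. The secondary objectives are to assess safety and tolerability of LOXO-305 alone and co-administered. SAP Section 8.6.1 summarises "TEAEs (overall, serious, and leading to discontinuation) by treatment", and also by day of onset and treatment. The SAP does not mention the timing of the inquiry.

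**The concern.** When solicitation follows vital signs, a gap in the vital signs schedule becomes a gap in adverse event ascertainment. The only timed same-day inquiry after a LOXO-305 dose is in the reference condition, at about the time of peak concentration (Protocol Section 1.4.2 gives a median tmax of approximately 2 hours, from steady-state data in patients). After a co-administered dose, an event that comes and goes within hours is recorded that day only if the subject volunteers it, staff notice it, or the site asks without being required to. Otherwise it depends on recall the next day.

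The sequence is fixed and non-randomised, so inquiry timing is fully confounded with treatment and cannot be separated from it in the analysis. Section 3.3 anticipates raised LOXO-305 exposure under inhibition, so the required inquiry is absent in a condition where early exposure-related events are of particular interest. At stake is the fair reading of early, transient TEAEs across the columns of a descriptive table.

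**Working it through.** The plan states no figure to reproduce, so the check counts what the schedule requires.

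**Inputs.** The timing rule (footnote g, both parts; Section 7.2.1), the vital signs times (footnote f, both parts) and the daily marks in the HDYF? row (Appendix 4).

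**Counting rule.** Required inquiries after a dose = (timed post-dose vital signs sets on the dosing day) + (one inquiry on each of the next 7 calendar days). An inquiry at an unspecified appropriate time on the dosing day is not counted as post-dose, because nothing requires it to follow the dose.

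| LOXO-305 dose | Vital signs on dosing day | Next vital signs | Required same-day post-dose inquiries | Next 7 days | Total |
|---|---|---|---|---|---|
| Part 1 Day 1, alone | predose and 2 h | Day 4 | 1 | Days 2–8: 7 | 1 + 7 = 8 |
| Part 1 Day 12, with itraconazole | predose only | Day 15 | 0 | Days 13–19: 7 | 0 + 7 = 7 |
| Part 2 Day 1, alone | predose and 2 h | Day 4 | 1 | Days 2–8: 7 | 1 + 7 = 8 |
| Part 2 Day 8, with first rifampin dose | predose only | Day 11 | 0 | Days 9–15: 7 | 0 + 7 = 7 |
| Part 2 Day 17, with repeated rifampin | predose only | Day 20 | 0 | Days 18–24: 7 | 0 + 7 = 7 |

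**Part 2 Day 8.** The single vital signs set that day is post-dose relative to Day 1 and predose relative to the co-administered dose. Read literally, the rule attaches that day's inquiry to this set, before the co-dose. If Day 8 is instead treated as a day with an inquiry at an appropriate time, a post-dose inquiry becomes possible but is still not required.

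**Other sources on the dosing day.** Footnote e gives the 12-lead ECG the same pattern: 2 hours on Day 1, predose only on Days 8 and 17 of Part 2 and Day 12 of Part 1. It does not fill the gap.

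**Windows in the SAP.** Under SAP Section 8.6.1, LOXO-305 alone covers Day 1 dosing to Day 8 dosing: 1 + 7 = 8 required inquiries.

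- Part 1 co-administration runs from Day 12 dosing: Days 13–19 give 7, plus the follow-up call, which asks only about serious and drug-related events.
- Part 2 assigns everything from Day 8 dosing onward to LOXO-305 and/or rifampin: Days 9–24 give 24 − 9 + 1 = 16, plus the call, spanning two LOXO-305 doses.

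The dosing-day gap thus runs one way, while the length of the Part 2 window runs the other.

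**The case against.** The strongest reply is that no interval goes unsolicited. Each inquiry reaches back to the previous one, the question is asked every day under every treatment, subjects are confined, and voluntary reporting is encouraged. The gap is one timed question per dose. The rule also does not forbid an inquiry after dosing, and a site may well ask one. All of this stands. It limits the effect to brief, mild, early events, but it does not make the requirement equal.

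Four stronger readings are tempting, and the documents do not support them.

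- *Co-administration will look better tolerated overall.* Early events are likely to be under-captured after a co-dose, but the Part 2 co-administration window in the SAP is longer and also collects events due to rifampin itself. The net direction for total TEAE counts is not established.
- *The bias can be put as a ratio of event rates.* The documents give neither an incidence of transient events in healthy subjects nor a capture rate with or without a timed question, and no such ratio is planned. The objectives are to assess tolerability, and SAP Section 8.6.6 excludes inferential analysis.
- *The sentinel review is undermined.* It covers all pertinent safety and tolerability data after the 3 subjects complete, including the Day 13–19 inquiries, the Day 15 and Day 19 ECGs and vital signs, and laboratory tests. It does not depend on the Day 12 inquiry.
- *The PK exclusion for vomiting rests on next-day recall.* The SAP allows exclusion "if the subject has an AE of vomiting that occurs at or before 2 times the median" tmax. Vomiting is overt, subjects are confined with supervised dosing, and the exclusion is discretionary. Serial PK draws imply further staff contact, although their detailed times are redacted.

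It can also be said that the root cause lies in footnote f, since a post-dose vital signs set would trigger the inquiry. That is true, but the inquiry can be put right by itself without adding measurements.

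**Conclusion.** The asymmetry is real and follows from the text: required same-day post-dose inquiries are 1 after LOXO-305 alone and 0 after each of the three co-administered doses, or 8 against 7 from the dose through the following 7 days. The first inquiry required after a co-dose is on the next calendar day. The likely consequence is that brief, mild events in the first hours are less completely captured, or less accurately timed, after co-administration. No size in event counts can be given from the documents, and the primary PK comparison is not affected.

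This rests on two assumptions: that redacted schedule text adds no post-dose inquiry on Part 1 Day 12 or Part 2 Days 8 and 17, and that the patient tmax of about 2 hours is a fair guide for healthy subjects. Priority is low: worth correcting because the correction is cheap.

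**What to change.** In footnote g of both parts and in Protocol Section 7.2.1, add an HDYF? inquiry approximately 2 hours after every LOXO-305 dose (Part 1 Days 1 and 12; Part 2 Days 1, 8 and 17), independent of vital signs, and keep the daily inquiry on all other days. This makes the required same-day count 1 for all five doses.

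The cost is one extra scripted question per Part 1 subject (Day 12) and two per Part 2 subject (Days 8 and 17), that is 12 × 1 + 12 × 2 = 36 questions at the planned enrolment. All subjects are already in the research unit, and no dose, blood draw or other measurement changes. The downside is slightly more minor adverse events recorded. If the protocol is not amended, a sentence in SAP Section 8.6.1 should state the difference in inquiry timing wherever TEAEs are set side by side by treatment; that discloses the inequality but does not remove it.

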1. INTRODUCTION

This SAP has been developed after review of the clinical study protocol (Final Version 1 dated 14 January 2020) and electronic case report form.

This SAP describes the planned analysis of the pharmacokinetic (PK), and safety and tolerability data from this study. A detailed description of the planned TFLs to be presented in the clinical study report (CSR) is provided in the accompanying TFL shells document.

In general, the analyses are based on information from the protocol, unless they have been modified by agreement with Loxo Oncology, Inc. A limited amount of information about this study (eg, objectives, study design) is given to help the reader's interpretation. This SAP must be finalized prior to the lock of the clinical database for this study. When the SAP and TFL shells are approved, they will serve as the template for this study's CSR.

This SAP supersedes any statistical considerations identified in the protocol; where considerations are substantially different, they will be so identified. If additional analyses are required to supplement the planned analyses described in this SAP, they may be performed and will be identified accordingly in the CSR. Any substantial deviations from this SAP will be agreed with Loxo Oncology, Inc. and identified in the CSR.

This SAP is written with consideration of the recommendations outlined in the International Conference on Harmonisation (ICH) E9 guideline *Statistical Principles for Clinical Trials* and ICH E3 guideline *Structure and Content of Clinical Study Reports*.^{1,2}

The document history is presented in Appendix 1.

2. STUDY OBJECTIVES

2.1. Primary Objectives

The primary objectives of this study are:

- To assess the impact of multiple oral doses of itraconazole (a strong cytochrome P450 [CYP]3A4 and P-glycoprotein [P-gp] inhibitor) on the single oral dose pharmacokinetics (PK) of LOXO-305 in healthy adult subjects.
- To assess the effect of multiple oral doses of rifampin (strong CYP3A4 inducer) on the single oral dose PK of LOXO-305 in healthy adult subjects.
- To assess the effect of a single oral dose of rifampin on the single oral dose PK of LOXO-305 in healthy adult subjects.

2.2. Secondary Objectives

The secondary objectives of this study are:

• To assess the safety and tolerability of a single oral dose of LOXO-305 when administered alone and co-administered with multiple oral doses of itraconazole.

• To assess the safety and tolerability of a single oral dose of LOXO-305 when administered alone and co-administered with single and multiple oral doses of rifampin.

3. STUDY ENDPOINTS

The following PK parameters will be calculated whenever possible, based on the plasma concentration of LOXO-305 (as appropriate):

- Area under the concentration-time curve from Hour 0 to 24 hours postdose, as calculated by the linear trapezoidal method (for Day 1 and Day 8 of Part 2 PK only [AUC₀₋₂₄])
- Area under the concentration-time curve from Hour 0 to the last measurable concentration (AUC_{0-t})
- Area under the concentration-time curve extrapolated to infinity (AUC_{0-inf})
- Extrapolation for area under the concentration-time curve (%AUC_{extrap})
- Maximum observed plasma concentration (C_{max})
- Time to maximum observed concentration (t_{max})
- Apparent terminal elimination rate constant (λ_Z also known as Kel)
- Apparent systemic clearance (CL/F)
- Apparent terminal elimination half-life $(t_{1/2})$

Safety and tolerability will be assessed by monitoring adverse events (AEs), performing physical examinations and clinical laboratory tests, measuring vital signs, and 12-lead electrocardiograms (ECGs).

4. STUDY DESIGN

This is a Phase 1, 2-part study. Each part will be conducted as an open-label, 2-period, fixed-sequence study. Following completion of the sentinel subjects in Part 1, the study parts may be conducted concurrently. Each subject will participate in either Part 1 or Part 2, but not both.

4.1. Part 1 – Itraconazole (CYP3A4 and P-gp Inhibitor)

In Part 1, Period 1, a single oral dose of 200 mg LOXO-305 will be administered in the morning of Day 1, following a fast of at least 10 hours prior to and 4 hours after dosing with LOXO-305. Blood samples for PK analysis of LOXO-305 in the absence of itraconazole will be taken up to 168 hours postdose of LOXO-305 on Day 1.

In Part 1, Period 2, multiple oral doses of 200 mg itraconazole will be administered twice daily (BID) on Day 8, and once daily (QD) from Day 9 until Day 18 inclusive (for a total of

11 consecutive days) and co-administered with a single oral dose of 200 mg LOXO-305 on Day 12 under fasted conditions. On Day 8, when itraconazole is administered BID, the morning dose will be administered alone at the actual time of the Day 1 LOXO-305 dose (\pm 1 hour), approximately 30 minutes after starting a standard breakfast, and the evening dose will be administered approximately 10 (\pm 1) hours after the morning dose, approximately 30 minutes after starting a standard evening meal. All meals should be entirely consumed within 30 minutes. On Days 9 to 11 and Days 13 to 18, the QD dose of itraconazole will be administered alone at the actual time of the Day 1 LOXO-305 dose (\pm 1 hour), approximately 30 minutes after the start of a standard breakfast, which should be entirely consumed within 30 minutes. On Day 12, a single oral dose of 200 mg LOXO-305 and a single oral dose of 200 mg itraconazole will be co-administered in the morning, following a fast of at least 10 hours prior to and 4 hours after dosing with LOXO-305 and itraconazole. Blood samples for PK analysis of LOXO-305 in the presence of itraconazole will be taken up to 168 hours postdose of the LOXO-305 dose on Day 12.

There will be a washout period of 7 days between the dose of LOXO-305 on Day 1 (Period 1) and the first dose of itraconazole on Day 8 (Period 2).

Part 1 will be divided into 2 cohorts; a sentinel cohort will comprise 3 subjects and the second cohort will comprise 9 subjects, for a total of 12 subjects.

Following completion of the sentinel cohort, the Investigator and Sponsor will review all pertinent safety and tolerability data (and PK data, if available) from the sentinel cohort before proceeding to dose the remaining 9 subjects in the second cohort in Part 1 of subjects in Part 2.

To assess their eligibility to enter the study, potential subjects will be screened within 28 days (Days -29 to -2) and be admitted to the Clinical Research Unit (CRU) on Day -1 (Check-in).

Subjects will be confined at the CRU from the time of Check-in (Day -1) until End of Treatment (EOT) on Day 19 upon completion of all PK and safety assessments or Early Termination (ET) if the subject discontinues. A follow-up phone call will occur for all subjects who received at least 1 dose of study drug (including subjects who are terminated early) 7 days (\pm 2 days) after EOT or ET.

Replacement subjects may be enrolled only if deemed necessary by the Sponsor.

